1. BACKGROUND AND SIGNIFICANCE

About 20,000 kidney transplants take place yearly in the US. Diabetes (DM) is the most common cause for end-stage kidney disease (ESKD) [1] and the most common clinical condition listed for kidney transplant (31%) [2]. Glucose levels are relatively controlled during ESKD (due to prolonged insulin action, reduced glycogen stores, decreased renal gluconeogenesis). Glycemic control is then disrupted in the early post-transplant period because these processes are reversed with the transplanted kidney, patients develop insulin resistance from high dose glucocorticoids and other anti-rejection medications, and their appetites increase [3].

Cleveland Clinic performs around 250 kidney transplants a year, and has successfully reduced the patients' length of hospital stay (LOS) post-transplant from 5 days down to 3 days by developing an enhanced recovery after surgery (ERAS) pathway that has a large outpatient diabetes management component. That is, patients no longer stay in the hospital to have their multiple daily insulin injection (MDII) doses adjusted. This necessitates having a reliable source of glucose readings when they are discharged to adjust their MDII doses and avoid hyperglycemia/hypoglycemia, and potentially reduce readmissions, rejection, and delayed graft function. Continuous glucose monitoring (CGM) is a method of measuring patients' glucose readings every 5-10 minutes via subcutaneous insertion of a sensor, reducing or even eliminating the need for painful fingerpricks (fingerpricks can be done as needed if there is discrepancy between the CGM reading and the patients' clinical scenario).

2. SPECIFIC OBJECTIVES:

1) Primary objective

To characterize the glucometrics (description of glucose readings in relation to target goals, as discussed in the Methods section), achieved by a CGM-based insulin titrating protocol for glucocorticoid taper for post kidney transplant patients

2) Secondary objective:

To explore the relationship between CGM glucometrics and rates of readmission, rejection, and delayed graft function in post kidney transplant patients

3. RESEARCH DESIGN AND METHODS

3.1 Primary endpoints

- 1) Ambulatory glucose profile (AGP) data glucometrics such as time in range, time below range, time above range, and glucose variability (coefficient of variation)
- 2) Readmission
- 3) Rejection
- 4) Delayed graft function

3.2 Secondary endpoints

- 1) Levels of HbA1c at 3 months and 6 months post-transplant
- 2) Diabetes medication adjustment at each time point (SEE schedule of assessments)

If YES, which of the following occurred (can be more than one answer)	
 reduction of any insulin dose stopped the scheduled insulin stopped the correction insulin stopped the basal insulin started a non-insulin medication
If NO, which of the following occurred (can be more than one answer)	
 stayed on the same insulin doses increased one or more insulin doses started a non-insulin medication without decreasing the dose of insulin

Categorical and continuous variables that will be collected closest to time of signed consent (last available recorded value for continuous variables):

- 1) Age
- 2) Sex
- 3) Weight
- 4) Height
- 5) BMI
- 6) HbA1c and serum glucose reading
- 7) Glucometrics based on CGM AGP, and individual CGM glucose reading download (Freestyle Libre readings are averaged every 5 minutes)
- 8) Serum creatinine
- 9) eGFR
- 10) Original kidney disease
- 11) Length of hospital stay for kidney transplant admission
- 12) Readmission (including reason)
- 13) Delay of graft function (defined as needing dialysis in the first 7 days post-transplant)
- 14) Rejection
- 15) Diabetes medication and dose
- 16) Appetite (qualitative: poor, fair, good, great)
- 17) Carbohydrate intake (dietary recall): grams of carbohydrate per meal
- 18) Prednisone taper schedule (standard upon inclusion but will note if changed to rapid)
- 19) Tacrolimus, other anti-rejection medication dose

Protocol Version 2, Dated 6-24-2024

20) Transferred to what type of provider (PCP/local endocrinologist/CCF endocrinologist) after 3 months

21) CGM upload (Enrollment –visit 10) with Abbott Libre. CGM upload (after visit 10) if patient has other CGM prescribed- percent of CGM time above range, in range, below range (TAR, TIR, TBR), or very high, high, in range, low, very low

22) Freestyle Libre or other CGM use pre and post-transplant

a) If not on CGM: what are the patients' reasons for not being on a CGM, or for not using consistently (e.g. insurance issues, durable medical equipment company delay, does not want to continue, no mobile app, provider not refilling/not incorporating into management)

b) If utilizing Freestyle Libre CGM, allow us to look at retrospective data OR patient to upload AGP from the previous visit. If patient on a different CGM, patient to upload AGP from previous visit.

3.3 Recruitment

A total of 20 patients that are post kidney transplant, will undergo intervention until 3 months post-transplant. Informed consent will be obtained prior to start of study. The final visit will be at 3 months. Patients will be discharged to their local endocrinologist or primary care physician at this 3-month mark. Data will continue to be gathered for 3 more months after exit from intervention.

Enrollment will be within the first 2 weeks of hospital discharge.

Screening of patients will be done through the inpatient endocrinology consult list (seen in various floors in the main campus hospital), or the endocrine kidney transplant clinic list (patients seen at Q8). Endocrine providers (physicians, nurse practitioners, pharmacists) who take care of qualifying patients will inform patients of this study at their visits again only mentioning a research study involving CGMs and kidney transplant patients. The endocrine providers will notify the study staff if the patient has questions or would like to learn more. The study staff will follow-up with the patients, provide and thoroughly review the consent. The patients will be given time to review the consent ask questions prior to making a decision to participate. The consenting process will take place in a private exam room if outpatient, or in the hospital room if still admitted to the hospital. The process will be documented in EPIC.

Visits are standard of care (SOC) at the Kidney Transplant Clinic or at the Endocrinology clinic and will be virtual or in-person or telephone encounter (see table). Visits are twice a week for the first 3 weeks post discharge. Following this, visits will be every two weeks until the end of the steroid taper(final steroid dose), usually 7.5mg daily by 56 days after transplant (see table below). This is part of SOC.

Standard prednisone taper	
Post op day	Prednisone dose
2	60 mg twice a day
3	50 mg twice a day
4	40 mg twice a day

5	30 mg twice a day
6	30 mg AM and 15 mg PM
7-13	30 mg in AM
14-27	20 mg in AM
28-41	15 mg in AM
42-55	10 mg in AM
56 and beyond	7.5 mg in AM

At Enrollment, insertion of Freestyle Libre 2 (or later version) sensor will be placed on upper arm. An account will also be set up on Libreview.com. This is part of SOC with diabetic patients who use CGMs. The patient will be asked to sign up on the product's platform (in this case for Freestyle Libre Abbott products, Libreview.com). We will be collecting data from the CGM ambulatory glucose profile (AGP) report or from phone/reader if we are unable to link to the patient's portal for certain visits. An insulin dosing protocol would be set up per patient. The patients would have already been seen by the inpatient endocrine team during the admission for their kidney transplant and would have been discharged on multiple daily insulin injection (MDII). This is part of the early recovery after surgery (ERAS) pathway that we have developed with the kidney transplant team. When patient is outpatient, we address dosing in order of priority by reducing or increasing the corresponding insulin by 10-100%. The range is wide to account for some doses that might be small (e.g. 2 units of rapid-acting insulin, for prednisone dose reduction, and for a change in appetite). We also make allowance for changing to non-insulin medications, as shown in the table.

Acceptable percentage of time that glucose levels are at a certain range, and insulin adjustment		
Glucose e and percentage of time it is acceptable for glucose levels to be in these ranges		Insulin adjustment by 10-100% (the range is wide to account for some doses that might be small, such as 2 units of rapid-acting insulin, for prednisone dose reduction, and for a change in appetite)
Time in very high range (>250mg/dL)	5% or less	Increasing the corresponding insulin if above 5%

Time in high (181-250 mg/dL) plus very high range	25% or less	Increasing the corresponding insulin if above 25%
Time In Range		
In range (70-180 mg/dL)	70% or greater	Continue to monitor but decrease if prednisone dose is decreasing
Time Below Range		
Time in low range (54-69 mg/dL) plus very low range	4% or less	Reducing the corresponding insulin if above 4% with option to reduce even if 4% or less (because we want to avoid further hypoglycemia)
Time in very low range (<54 mg/dL)	1% or less	Reducing the corresponding insulin if above 1% with option to reduce even if 1% or less (because we want to avoid further hypoglycemia)
Other insulin protocols		
Serum creatinine or eGFR is still elevated		Dose adjustments will be towards giving less insulin
Attempt to stop mealtime insulin and substitute with medication below		
Prednisone dose is 10mg daily or less	CGM shows >70% time in range	There is no contraindication to the medication to be started
Keep or reduce basal insulin. Keep the correction scale insulin while initiating medication changes below. Order with which medication switch is to be made; proceed to the next one on the list if there is contraindication or plan restriction.		

- 1. GLP-1 agonist
- 2. DPP-4 inhibitor
- 3. Sulfonylurea
- 4. Unable to use the other DM medication types yet at this early phase post-transplant

Stop correction scale insulin. As allowed by CGM pattern, increase basal insulin if needed to eliminate correction scale insulin.

Next attempt is to stop the basal insulin by increasing the dose of the GLP-1 agonist or DPP-4 inhibitor or sulfonylurea, or addition of a sulfonylurea to the GLP-1 agonist or DPP-4 inhibitor.

Outline of procedures

Events	Enrollment	Visit 1	Visit 2	Visit 3	Visit 4	Visit 5	Visit 6	Visit 7	Visit 8	Visit 9	Visit 10	Visit 11	Visit 12
Time points	within 2 weeks of hospital dis-charge	1 week post discharge +/-3 days*	2 weeks post discharge +/-3 days*	3 weeks post discharge +/-3 days*	Week 5 +/-3 days*	Week 7 +/-3 days*	Week 9 +/-3 days*	Week 12 (3 mo) +/- 1 month	Week 18 (4.5 months)	Week 24 (6 mo) +/- 1 month			
	In-person	In-person or virtual					Telephone encounter (unless patient wants an in-person or virtual visit)			In-person preferred, virtual if needed	Telephone encounter (unless patient wants an	Telephone encounter (unless patient	

											in-person visit)	wants an in-person visit)
Consent	X											
Libreview Account Set-up, CGM insertion, CGM teaching	X											
CGM download	X	X	X	X	X	X	X	X	X	X	X ^{a2}	X ^{a2}
Demographics - age, sex, weight, height (height only on enrollment), BMI	X	X	X	X	X	X	X	X	X	X	X	X
Labs - serum crea/eGFR/serum glucose Optional for some visits, but these are SOC	X	X	X	X	X	X	X	X	X	X	X	X
HbA1c	X									X		X
Appetite evaluation (poor, fair, good, great)	X	X	X	X	X	X	X	X	X	X	X	X
Carbohydrate intake	X	X	X	X	X	X	X	X	X	X	X	X

(approximate grams, dietary recall)													
Diabetes medication review	X	X	X	X	X	X	X	X	X	X	X	X	X
Transplant medication review	X	X	X	X	X	X	X	X	X	X	X	X	X
Ambulatory glucose profile (AGP) and individual glucose reading downloads		X	X	X	X	X	X	X	X	X	X	X ^b	X ^b
Document - Readmission/rejection/ delayed graft function		X	X	X	X	X	X	X	X	X	X	X	X

Note: All visits and labs are Standard of Care (SOC). Serum crea/eGFR are ordered by the kidney transplant team. A1c is ordered by the endocrine team.

*Window variances measured in business days

a For those who remain on it; fingerstick for those who do not

b If still on CGM; survey if not on CGM

3.4 Statistical Methods

The goal of the present study is not hypothesis testing, but rather estimation. With 20 patients, and assuming that the standard deviation in the time in range will be no more than 20%, and time in range levels will be moderately correlated over time ($r = 0.5$), estimated changes in time in range will be estimated to within $\pm 9.4\%$. Additionally, there will be at least 80% power to detect mean changes of at least 13.3% in time in range over time within patients. This sample size will allow us to generally estimate precision of the prevalence of binary events such as readmission and delay of graft function to within $\pm 20\%$ provided that the event rate is less than 30%.

Patient characteristics will be summarized overall and by group using means and standard deviations for continuous measures and frequencies and percentages for categorical factors. Medication adjustment as well as binary events such as readmission, rejection and delayed graft function rates will be estimated at each time point and compared over time using McNemar tests or generalized mixed effect models. To evaluate continuous measures such as HbA1c and AGP metrics over time, paired t-tests or linear mixed models will be used. In these models, time will be the main predictor. Estimated HbA1c and glucometrics levels at each time with 95% confidence limits will be estimated from the model. Linear mixed models are valid under the assumption of missing at random. This will be evaluated graphically and, if necessary, sensitivity analyses will be performed to evaluate the potential effects of the missing data over time. If glucometric time measures are close to the extremes of the distribution (i.e. near 0 or 1), then an alternate approach using beta regression to estimate the levels and changes may be performed. Time to readmission and rejection will be estimated using Kaplan-Meier analysis. If interim analyses result in a change to the insulin dosing protocol, results will be presented overall, and then separately for the first 10 and last 10 patients. Stratification of results may also be performed based on the timing of enrollment relative to the transplant. Analysis will be performed using SAS software (version 9.4; Cary, NC) or R software (version 4.1; Vienna, Austria). Given that this is a pilot study, we will perform all tests using a 0.05 significance level, and focus on estimation to allow for future research, if warranted.

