4. STUDY POPULATION

This is a non-randomized perspective single arm study with a planned enrollment of 20 patients.

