A file database will be created for data collection accessible only by authorized study personnel. Information will be entered into the database as it is collected and patients finish the study. Each patient will be assigned a study number consecutively as they are enrolled. Only the study number will be used to identify all study-related documents such as case report forms. A master list of study numbers linked to patient identifiers will be maintained by the study coordinator in a secured location. Study data will be collected and managed using REDCap (Research Electronic Data Capture); this will include patient identification number, medical record number, age, gender, and ethnicity.

If a subject withdraws from the trial or is lost to follow-up, then the subject's data which has already been collected will be retained by the investigator, entered into the database and used for the study reporting.

6. ETHICS:

Protocol Version 2, Dated 6-24-2024

The study will be conducted in compliance with ICH GCP and applicable regulatory requirements, and in accordance with the Declaration of Helsinki.

Voluntary signed informed consent will be obtained from each study subject prior to initiating any research interventions. Informed consent will be documented in the subject's medical record.

This study is subject to the review and approval of the Cleveland Clinic Institutional Review Board prior to initiating any study activities.

7. PUBLICATION PLAN:

Upon study completion, the data generated will be submitted in abstract form to an endocrine-, diabetes-, or kidney transplant-related meeting, and subsequently submitted to a journal for consideration for publication.

8. CITATIONS:

Burrows NR et al. Reported Cases of End-Stage Kidney Disease — United States, 2000–2019. MMWR Recomm Reports. 2022;71(11):412-415

Hart A et al. OPTN/SRTR 2019 Annual Data Report. Am J Transplant 2021;21(2):21-137

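### Do the ±9.4% precision and 80% power for change in time in range fail because no allowance is made for lost or missing pairs?

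*Protocol*

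**What the plan says.** Section 3.4 declares estimation, not hypothesis testing, as the goal. It supports the sample size with a calculation for 20 patients, "assuming that the standard deviation in the time in range will be no more than 20" percent, and a within-patient correlation of 0.5. From these inputs, "estimated changes in time in range will be estimated to within" ±9.4%, and "there will be at least 80% power to detect mean changes of at least 13.3% in time in range over time within patients". The two time points being compared are not named. The listed analyses are paired t-tests or linear mixed models, with sensitivity analyses for missing data if needed.

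Section 4 describes a "single arm study with a planned enrollment of 20 patients". Section 5 covers the case "If a subject withdraws from the trial or is lost to follow-up" by keeping and using the data already collected.

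On timing, Section 3.3 states "Enrollment will be within the first 2 weeks of hospital discharge". It also states "At Enrollment, insertion of Freestyle Libre 2 (or later version) sensor will be placed on upper arm". The first post-discharge time point in the outline of procedures is "1 week post discharge +/-3 days", counted in business days. Section 3.2, item 22b, allows retrospective data from patients who use a Libre sensor, and Section 3.3 allows consent in the hospital room before discharge.

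**The concern.** The number in the calculation equals the number to be enrolled, so there is no margin. The protocol itself foresees withdrawal and loss to follow-up. If the figures need all 20 patients at both time points, one loss would make the ±9.4% and the 80% too favourable.

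The schedule adds a second worry. The sensor may go on as late as 14 days after discharge, while the week-1 window closes at about day 10 to 12 (day 7 plus 3 business days, depending on the weekday). A patient enrolled after that, with no earlier Libre data, has no week-1 time in range even if nobody drops out. Because no time points are named, a reader could take ±9.4% to cover a change from week 1.

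Precision is one of the two reasons given for choosing 20 patients (the other is ±20% for binary events). An overstated figure would therefore weaken the case for the sample size.

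**Working it through.** **Inputs (Section 3.4).** n = 20, SD = 20 points (upper bound), r = 0.5, significance level 0.05. Two-sided testing is assumed; it reproduces the stated figures.

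**Step 1: reproduce the stated figures.**
- SD of change = 20 × √(2 × (1 − 0.5)) = 20.
- Half-width = t(0.975, 19) × 20/√20 = 2.093 × 4.472 = 9.36, stated as 9.4.
- Power for 13.3 points, from the noncentral t with 19 df and noncentrality 13.3/4.472 = 2.97, is 80.5%, stated as at least 80%.

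Both agree, so there is no arithmetic error.

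**Step 2: fewer complete pairs, paired t-test, SD of change held at 20.** The last two columns give the largest SD of change at which each stated figure still holds.

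| Pairs | Half-width | Power at 13.3 | Largest SD for ±9.4 | Largest SD for 80% power |
|---|---|---|---|---|
| 20 | 9.36 | 80.5% | – | – |
| 19 | 9.64 | 78.3% | 19.5 | 19.6 |
| 18 | 9.95 | 75.8% | 18.9 | 19.0 |
| 16 | 10.66 | 70.1% | 17.6 | 17.7 |

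Each lost pair costs about 0.3 to 0.4 points of half-width and 2 to 3 points of power at the bound. If the SD lies modestly under the bound, both figures survive.

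**Step 3: the mixed model that Section 3.4 also lists.** Assume compound symmetry with r = 0.5, SD 20, ten visits (Visits 1 to 10) and pooled residual df = 9 × (n − 1). For complete patients the standard error of a difference between two visits is again 20/√n, but the t quantile is smaller.

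| Patients | df | Half-width | Power at 13.3 |
|---|---|---|---|
| 20 | 171 | 1.974 × 4.472 = 8.83 | 84% |
| 19 | 162 | 1.975 × 4.588 = 9.06 | 82% |
| 18 | 153 | 1.976 × 4.714 = 9.31 | 80.1% |

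Under these assumptions both stated figures stand after two patients are lost entirely, even at the SD bound. With df set to pairs minus 1 they do not; the result is then that of Step 2.

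**Step 4: patients missing week 1 only.** The protocol gives no distribution of enrolment timing, so the counts below are assumptions. The model is that of Step 3, for the first-to-last contrast. The mixed-model range runs from pooled df to complete pairs minus 1.

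| Missing week 1 | Standard error | Mixed-model half-width | Paired t half-width |
|---|---|---|---|
| 2 of 20 | 4.61 | 9.1 to 9.7 | 9.95 |
| 5 of 20 | 4.87 | 9.6 to 10.4 | 11.1 |
| 10 of 20 | 5.57 | 11.0 to 12.6 | 14.3 |

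A contrast that starts at week 1 could be noticeably less precise if many patients enrol late. The protocol neither names that contrast nor indicates how many would.

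**The case for a change.** The strongest case for a change is that an SD of at most 20 paired with power of at least 80% reads as a guarantee at the bound. At the bound, with a paired t-test, that guarantee fails with the first lost pair. The schedule also allows missing week-1 data under perfect retention, in the period when the prednisone taper is at its higher doses. The cost of correction is two or three sentences, and estimation is the declared purpose.

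Part of this stands. The calculation does assume data at both compared times for all 20 patients, and the text does not say so. Contrasts from week 1 may rest on fewer patients.

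The rest does not carry. The statement is conditioned on 20 patients, an SD and a correlation, and a reader would ordinarily take 20 patients to mean 20 analysed. Choosing the time points of a contrast is commonly left to the SAP, which is not at hand. Retrospective sensor data and consent before discharge both reduce the week-1 gap by an amount the protocol does not let one calculate. Adding only the paired-test figures for 18 and 16 pairs would understate what the listed mixed model may deliver. Tying the headline figure to a later contrast, such as week 3 to week 12, would leave out the early taper and still be exposed to dropout.

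**Conclusion.** No change follows. The ±9.4% and the 80% power for 13.3% are correctly computed for 20 patients with time in range at both compared times, at the upper-bound SD and r = 0.5. Losing two pairs moves the paired-test result to ±9.95 and 76%. Under the mixed model with compound symmetry and pooled df, the loss of two patients leaves both stated figures intact. The document gives no loss rate, no enrolment timing and no week-1 contrast, so it does not show that the design misses a stated figure.

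The remaining gap is an implicit complete-data assumption in a planning sentence. Filling it would not affect who is enrolled, what is measured, how it is analysed or what is concluded, and the final confidence intervals will show the precision actually achieved. This rests on the protocol's own SD bound and correlation. If half the patients lacked week-1 data and a week-1 contrast were reported, its half-width would be about 11 to 14 points, and the reported interval would show it.

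### Readmission and rejection rates are compared across visits with very unequal time at risk, so a constant risk would show as a rise of about 6- to 12-fold

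*Protocol*

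**What the plan says.** Section 3.1 lists readmission, rejection and delayed graft function among the primary endpoints. Section 3.4 groups medication adjustment with "binary events such as readmission, rejection and delayed graft function rates" and says that these "rates will be estimated at each time point and compared over time using McNemar tests or generalized mixed effect models". It mentions no person-time denominator, offset or common interval. It separately plans Kaplan-Meier estimates of time to readmission and to rejection.

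The schedule is in Section 3.3. "Visits are twice a week for the first 3 weeks post discharge"; visits are then two-weekly to the end of the taper (weeks 5, 7 and 9), followed by "Week 12 (3 mo) +/- 1 month", week 18 and "Week 24 (6 mo) +/- 1 month". The table row "Document - Readmission/rejection/ delayed graft function" is marked at each of Visits 1 to 12, without saying whether an entry covers events since the previous visit or all events so far. The table's row of time points carries nine labels for these twelve visits (weeks 1, 2, 3, 5, 7, 9, 12, 18 and 24), so the twice-weekly visits share weekly labels.

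Section 3.2 defines delayed graft function by dialysis within seven days of transplantation.

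**The concern.** A state such as time in range or current medication can be compared from one visit to the next. The number of patients with a new event cannot, unless the intervals are of equal length or the analysis accounts for their length. McNemar's test has no place for exposure. A generalized mixed model could carry an offset, but none is stated.

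The direction of the distortion makes it easy to misread. The short intervals fall early, while prednisone is being tapered from its higher doses. The two six-week intervals fall after Visit 10, when patients have been handed over to local care. A flat risk would therefore look, in the per-visit rates, like a deterioration after handover.

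**Working it through.** **The plan's own binary figure.** Section 3.4 gives a precision of about ±20% for event rates below 30%. At 30% with n = 20, 1.96 × √(0.30 × 0.70 / 20) = 0.201, which agrees. This figure describes one proportion and says nothing about comparing proportions over unequal intervals.

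**Intervals.** Taking visits at nominal times from discharge, the gaps in days are 3.5 (six times), 14, 14, 14, 21, 42 and 42. On the weekly labels the first gaps are 7 days. The longest-to-shortest ratio is 42 / 3.5 = 12 by visit, or 42 / 7 = 6 by label.

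**Reading 1: events since the last visit.** The Protocol gives no expected event rate, so the 24-week risk P is an assumption, varied from 10% to 50%. With a constant hazard, h = −ln(1 − P) / 24 per week, and the risk in an interval of w weeks is 1 − exp(−h·w). For P = 30%, h = 0.3567 / 24 = 0.01486. The risks are 0.74% for half a week, 1.48% for one week, 2.93% for two, 4.36% for three and 8.53% for six.

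| Assumed P | Half week | One week | Six weeks | Six weeks ÷ half week | Six weeks ÷ one week |
|---|---|---|---|---|---|
| 10% | 0.22% | 0.44% | 2.60% | 11.9 | 5.9 |
| 20% | 0.46% | 0.93% | 5.43% | 11.7 | 5.9 |
| 30% | 0.74% | 1.48% | 8.53% | 11.5 | 5.8 |
| 50% | 1.43% | 2.85% | 15.91% | 11.1 | 5.6 |

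The ratio hardly depends on P. It reflects interval length alone.

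**Expected counts.** In 20 patients at P = 30%, 0.148 patients have an event in a half-week interval and 1.706 in a six-week interval. Divided by nominal patient-weeks, these are 0.148 / (20 × 0.5) = 0.0148 and 1.706 / (20 × 6) = 0.0142 per patient-week. Once exposure is in the denominator the apparent rise disappears; the small remaining gap arises because nominal weeks ignore that time at risk ends at a first event.

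**Chance of false significance on Reading 1.** Treating the two intervals as independent, an exact McNemar test of a half-week against a six-week interval reaches two-sided 0.05 with probability 0.5% at P = 30% and 6.7% at P = 50%.

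**Reading 2: events to date.** A patient with an event by one visit still has it at the next. The proportion cannot fall, and every discordant pair points the same way. Week 24 against the first half-week visit gives 0.30 / 0.0074, about 40-fold, at P = 30% (35- to 46-fold over the range). Here a small p-value is easier to reach: six discordant pairs in one direction give 2 × 0.5⁶ = 0.031, and 30% of 20 patients is six. It would show only that events had accumulated.

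**Delayed graft function.** By its definition it is fixed for each patient once day 7 after transplantation has passed. With the three-day stay described in Section 1, at most the earliest visit could precede that day. There is no later change for a comparison over time to find.

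**The case against.** Four points can be made for the plan.

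- **The size depends on the reading.** Section 3.4 speaks of time points, not visits, and the table's labels are weekly in the first three weeks. A reader might take 12-fold as the established size. The documents do not support that: it needs both the per-visit and the since-last-visit reading, and the weekly labels give about 6-fold. Both figures also compare only the extreme intervals.
- **The detail may be in the SAP.** The look-back window and a model offset could be settled there. That is fair for the offset. But the Protocol itself fixes a rate at each time point, a comparison over time, and McNemar's test as one option, and that test cannot use an offset.
- **Kaplan-Meier is already planned.** This stands. A reader might infer that a real early excess would be hidden. It would not: the curves for readmission and rejection would fall steeply early on. However, that analysis is additional, so the per-visit comparison would still be produced alongside it.
- **Few events.** A reader might also infer that the trial will report a significant late rise. On the since-last-visit reading that is unlikely, as the probabilities above show. The objection does not rescue the estimates, because Section 3.4 puts estimation ahead of testing and the estimated trend is what is distorted.

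**Conclusion.** The point holds. As written, the comparison over time of readmission and rejection follows the visit schedule rather than risk. A constant hazard would appear as a rise of about 6-fold on the weekly labels or about 12-fold on twice-weekly visits if events are counted since the last visit; if counted to date, the proportion can only increase. For delayed graft function the comparison has no content after the first week.

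The figures assume nominal visit times, a constant hazard and a 24-week risk of 10% to 50%. Visit windows, and enrolment up to two weeks after discharge, would make actual exposure vary further.

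The damage is to the estimated trend for listed primary endpoints. It is limited by the planned Kaplan-Meier curves, and the documents do not show that a false late rise would be declared or an early excess missed. The change is worth making because it is cheap.

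**What to change.** In Section 3.4:

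1. Restrict the visit-to-visit McNemar or mixed-model comparison to medication adjustment.
2. Report delayed graft function once, as a proportion with an exact 95% interval.
3. For readmission and rejection, use the planned Kaplan-Meier cumulative incidence to describe timing.
4. If rates by period are wanted, give events per patient-week with exact Poisson 95% limits in a few fixed periods, counted from one stated origin (transplantation or discharge). Alternatively, keep a model of events since the last visit with log interval length as an offset. For a binary outcome, a complementary log-log link makes that offset correct under a constant hazard.

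The cost is analysis wording only, since Kaplan-Meier already requires event dates. The downside is imprecision: at an assumed 30% risk, about 20 × 0.30 = 6 patients would have a first event over 24 weeks, so limits within any one period will be wide.
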